13.4.1 Adverse Events

Adverse events will be summarized by dose, Medical dictionary for medical activities (MedDRA) terminology (latest version), severity and relation to study drug. The descriptive statistics presented for each system-organ class and preferred term will be the number of subjects with event (N), the percent of subjects exposed with event (%), and the number of events (E). All AEs will be listed by subject, including demographic information, dose, MedDRA latest version, system organ class, and preferred term.

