10. SAFETY

Adverse Events

An AE is defined as any untoward medical occurrence in a subject administered a medicinal product and which does not necessarily have to have a causal relationship with this treatment. An AE can therefore be any unfavorable and unintended sign (for example, an abnormal laboratory finding), symptom, or disease temporally associated with the use of a medicinal product, whether or not considered related to this medicinal product.

A suspected adverse reaction is any AE for which there is a reasonable possibility that the drug caused the AE. 'Reasonable possibility' means there is evidence to suggest a causal relationship between the drug and the AE. A suspected adverse reaction implies a lesser degree of certainty about causality than adverse reaction, which means any AE caused by a drug.

AEs occurring after the initiation of the treatment are referred to as treatment emergent adverse events (TEAEs).

TEAEs will be assigned to a treatment based on the time of occurrence in relation to the last treatment administered prior to the onset of the TEAE. TEAEs will be assigned using the following rules:

- TEAE will be assigned to the last treatment taken by the subject where the date and time of the last treatment dosing is on or before of the start date and time of the event. Such assignment will be performed irrespective of any washout period between the start and stop dates of the TEAE.
- Any TEAE started after the discharge and during the follow-up period will be assigned to the last treatment that the subject has taken during last period.

As an overall summary of AEs, the following will be presented by treatment and overall:

- Number of reported AEs;
- Number of reported TEAEs;
- Number and percentage of subjects experiencing TEAEs;
- Number and percentage of subjects experiencing a drug-related TEAE (i.e. those with a relationship classified as reasonable possibility)
- Number and percentage of TEAEs by relationship to study treatment (i.e. reasonable possibility, no reasonable possibility);
- Number and percentage of TEAEs by severity;
- Number of reported SAEs (serious adverse events);
- Number and percentage of subjects experiencing SAEs;
- Number and percentage of subjects experiencing drug-related SAEs;
- Number and percentage of TEAEs leading to withdrawal; and
- SAEs with an outcome of death.

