Frequency tables will be presented by treatment, system organ class and preferred term that summarize all Treatment Emergent Adverse Events (TEAEs), and SAEs. Frequency tables will also be presented by treatment, system organ class, preferred term and maximum severity and by treatment, system organ class, preferred term and relationship to study drug.

Subject listings of all Adverse Events (AEs) including severity and relationship to study drug will be provided. AEs leading to withdrawal and SAEs will also be presented in separate listings.

Concomitant Medications

Medications taken after the first dose of study drug until after discharge from the study will be recorded. Concomitant medications will be presented in a listing. The medication name, active ingredient, dose, units, formulation, route, indication or reason taken, code, date and time taken will be presented. The listing will also include the coding terms (e.g., ATC and Preferred Term).

Extent of Exposure

Details of drug dosing (actual treatment received, actual date and time of administration, dose administered, and route of administration) will be listed by subject.

Clinical Laboratory Evaluations

Planned laboratory analyses include:

- Blood Chemistry: alkaline phosphatase (ALP), alanine aminotransferase (ALT), aspartate aminotransferase (AST), total and direct bilirubin, blood urea nitrogen (BUN), creatinine, gamma glutamyltransferase (GGT), glucose, potassium, sodium;
- Hematology: hemoglobin, hematocrit; platelets, prothrombin time (PT), red blood cells (RBC), white blood cells (WBC) with differential (absolute),
- Urinalysis: bilirubin, erythrocytes, glucose, ketones, leukocytes, nitrite, pH, protein, specific gravity, urobilinogen
- Other: urine drug screen and serum pregnancy.

Hematology, chemistry and quantitative urinalysis laboratory test results, as well as the change from baseline, will be summarized by sequence, parameter and visit.

Separate listings of all individual data for urinalysis, hematology, chemistry and other laboratory tests will be presented by subject, laboratory test and visit.

Subject listings of abnormal on-study laboratory values will be provided, including demographic information. Similarly, clinically significant on-study laboratory data will be presented in a second listing.

Vital Signs

Vital signs will include the measurement of blood pressure, heart rate, oral temperature, and body weight.

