12. CHANGES TO PROTOCOL-SPECIFIED ANALYSES

There is no change from the planned analysis described in the protocol.

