Diff in # of Collisions		Lasmiditan 50 mg vs PBO	Lasmiditan 100 mg vs PBO	Lasmiditan 200 mg vs PBO	Alprazolam 1 mg vs PBO
N		xx	xx	xx	xx
Mean		x.x	x.x	x.x	x.x
SD		x.xx	x.xx	x.xx	x.xx
Median		x.x	x.x	x.x	x.x
Min, Max		xx, xx	xx, xx	xx, xx	xx, xx
p-value*		0.xxxx	0.xxxx	0.xxxx	0.xxxx
Diff in # of Collisions		Lasmiditan 50 mg vs Alprazolam 1 mg	Lasmiditan 100 mg vs Alprazolam 1 mg	Lasmiditan 200 mg vs Alprazolam 1 mg	
N		xx	xx	xx	
Mean		x.x	x.x	x.x	
SD		x.xx	x.xx	x.xx	
Median		x.x	x.x	x.x	
Min, Max		xx, xx	xx, xx	xx, xx	
p-value*		0.xxxx	0.xxxx	0.xxxx	

*Wilcoxon Signed Ranks test.

{Repeat table for off-road crashes (Table 14.2.4.14), and total collisions (Table 14.2.4.15)}

SAS Program Name:

Date:

Source Data: Listing 16.2.6.X

Table 14.3.1.1
Summary of Adverse Events
(Safety Population)

	Placebo (N=XX)	Lasmiditan 50 mg (N=XX)	Etc.	Overall (N=XX)
Adverse Events (AEs) Reported [n]				XX
Treatment Emergent Adverse Events (TEAEs) Reported [n]	XX	XX	XX	XX
Subjects With At Least One TEAE [n(%)] [1]	XX (XX.X)	XX (XX.X)	XX (XX.X)	XX (XX.X)
Subjects With At Least One Drug-Related TEAE [n(%)] [1] [3]	XX (XX.X)	XX (XX.X)	XX (XX.X)	XX (XX.X)
TEAEs Relationship [2]				
Reasonable Possibility [n (%)]	XX (XX.X)	XX (XX.X)	XX (XX.X)	XX (XX.X)
No Reasonable Possibility	XX (XX.X)	XX (XX.X)	XX (XX.X)	XX (XX.X)
TEAEs Severity/Intensity [2]				
Mild [n(%)]	XX (XX.X)	XX (XX.X)	XX (XX.X)	XX (XX.X)
Moderate [n(%)]	XX (XX.X)	XX (XX.X)	XX (XX.X)	XX (XX.X)
Severe [n(%)]	XX (XX.X)	XX (XX.X)	XX (XX.X)	XX (XX.X)
Life-Threatening [n(%)]	XX (XX.X)	XX (XX.X)	XX (XX.X)	XX (XX.X)
Serious Adverse Events (SAEs) Reported [n] [2]	XX	XX	XX	XX
Subjects With At Least One SAE [n(%)] [1]	XX (XX.X)	XX (XX.X)	XX (XX.X)	XX (XX.X)
Subjects With At Least Drug-Related SAE [n(%)] [1]	XX (XX.X)	XX (XX.X)	XX (XX.X)	XX (XX.X)
Subject With a TEAE Leading to Withdrawal [n(%)] [1]	XX (XX.X)	XX (XX.X)	XX (XX.X)	XX (XX.X)
Death [n(%)] [1]	XX (XX.X)	XX (XX.X)	XX (XX.X)	XX (XX.X)

[1] Percentages are based on the number of subjects in the Safety population in each treatment group.

[2] Percentages are based on the total number of treatment emergent adverse events reported in each treatment group.

[3] TEAE that was reported with a relationship of "reasonable possibility".

Date: VERSION - YYYY-MM-DD

Data Source: XXXX

Program Source: XXXXX.sas

Table 14.3.1.2
Summary of Treatment Emergent Adverse Events by System Organ Class and MedDRA Preferred Term
(Safety Population)

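### The AE overview gives severity only as a share of each treatment's own TEAEs, which can rank treatments against the per-subject risk, and no planned table shows the percentage of subjects with a severe TEAE across all terms

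*SAP*

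**What the plan says.** SAP section 10, under Adverse Events, plans an overview by treatment and overall. Its severity item is "Number and percentage of TEAEs by severity".

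The shell for this overview is Table 14.3.1.1 in SAP Appendix B. Its severity block carries footnote [2]: "Percentages are based on the total number of treatment emergent adverse events reported in each treatment group". The relationship block carries the same footnote. The rows for any TEAE, any drug-related TEAE, any SAE, any drug-related SAE, a TEAE leading to withdrawal, and death carry footnote [1] instead: "Percentages are based on the number of subjects in the Safety population in each treatment group". Relationship therefore appears both by event and by subject, while severity appears only by event.

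One further severity table is planned: "Frequency tables will also be presented by treatment, system organ class, preferred term and maximum severity". In its shell, Table 14.3.1.4, the top row (subjects with any TEAE) and the system organ class rows each show a single n (%). The severity grades appear only beneath a preferred term.

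On withdrawal, the SAP section 10 bullet counts TEAEs, whereas the Table 14.3.1.1 row counts subjects on the footnote [1] denominator.

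**The concern.** A percentage of events is not a risk. Its denominator is itself an outcome of treatment: a treatment that adds many mild events enlarges the denominator and so lowers its own severe percentage. Protocol section 6.1 names dizziness and fatigue as the most common adverse events with lasmiditan and as the reason for the study, so larger TEAE totals on the active treatments are plausible. Protocol section 12.1.1 grades severity by limitation of usual activities, which bears on what a driving study wants to know.

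The overview is the only planned place where severity is shown by treatment across all terms together. If its percentage falls as the per-subject risk rises, someone reading down the percentage column compares the treatments the wrong way round. The statistic that would correct this is not planned.

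**Working it through.** **Inputs.** The documents state no adverse-event rate, so there is no plan figure to reproduce. From the documents: the two denominators in the Table 14.3.1.1 footnotes, and about 80 subjects per treatment (SAP section 3: 80 completers, each receiving all five treatments). All event counts below are assumptions made for illustration.

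**Formulas.** For one treatment, let T be the total TEAEs, s the severe TEAEs, m the subjects with at least one severe TEAE, and N the subjects dosed.

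- Planned overview percentage: 100 × s / T.
- Per-subject percentage: 100 × m / N.

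Between an active treatment (a) and placebo (p), the planned percentage is lower on the active treatment whenever T_a / T_p exceeds s_a / s_p, whatever the per-subject risks are.

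**Two-treatment example.** N = 80, one severe event per affected subject.

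- Placebo, T = 10, s = 1: 1/10 = 10.0% of events; 1/80 = 1.25% of subjects.
- Lasmiditan 200 mg, T = 60, s = 4: 4/60 = 6.7% of events; 4/80 = 5.0% of subjects.
- Condition: 60/10 = 6 exceeds 4/1 = 4, so the order reverses. The subject ratio is 5.0/1.25 = 4.

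**Five-treatment example.** N = 80.

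| Treatment | TEAEs | Severe TEAEs | Subjects with severe | % of events | % of subjects |
|---|---|---|---|---|---|
| Placebo | 12 | 1 | 1 | 8.3 | 1.25 |
| Lasmiditan 50 mg | 40 | 2 | 2 | 5.0 | 2.50 |
| Lasmiditan 100 mg | 70 | 3 | 3 | 4.3 | 3.75 |
| Lasmiditan 200 mg | 120 | 5 | 5 | 4.2 | 6.25 |
| Alprazolam 1 mg | 110 | 5 | 4 | 4.5 | 5.00 |

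The treatment with the most TEAEs and the most subjects with a severe event shows the lowest severe percentage.

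**Range.** Against placebo at 1/12 = 8.3%, a treatment with 60, 120 or 200 TEAEs still prints a lower percentage with up to 4, 9 or 16 severe TEAEs. At one per subject that is 4/80 = 5.0%, 9/80 = 11.25% or 16/80 = 20.0% of subjects, against 1.25%. The reversal is not inevitable: with 60 TEAEs and 6 severe, 6/60 = 10.0% is above 8.3% and the order agrees with the subject percentages.

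**Can the missing figure be built from Table 14.3.1.4?** No. One subject may have severe events under several terms. Three preferred terms with 2 severe subjects each are compatible with anything from 2/80 = 2.5% (the same two people) to 6/80 = 7.5% (six different people).

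**Can it be read from the overview counts?** Only as bounds. Four severe events may lie in one to four subjects, that is 1/80 = 1.25% to 4/80 = 5.0%.

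**The case against.** The strongest reply is that the table is transparent. Each severity cell prints a count beside the percentage, the column header gives N, and the footnote states the denominator. In the first example the cells would read 1 (10.0) and 4 (6.7), each under N = 80. In a full crossover the Ns should be close, so the counts compare directly. This stands and limits the harm. It does not supply the number of subjects, which the event counts only bound.

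Subject-level severity is also planned per preferred term in Table 14.3.1.4, and so for dizziness and fatigue individually, and the adverse-event listing carries severity. This too stands: the all-term figure could be derived from the data. It is simply not among the planned tables.

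The Table 14.3.1.4 shell is abbreviated. Several of its preferred terms also lack grade rows, and SAP section 13 allows slight layout changes and additional tables. A top-line split could therefore be added without difficulty, but neither the SAP text nor any shell calls for one.

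The reversal rests on assumed counts, no between-treatment test of adverse events is planned, and the share of events by severity is a legitimate, labelled description. All of that is correct.

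A reader might go further and infer that the SAP departs from protocol section 13.4.1, which defines the adverse-event percentage on exposed subjects, while SAP section 12 declares "There is no change from the planned analysis described in the protocol". The documents do not support this. Section 13.4.1 attaches those statistics to each system organ class and preferred term, and the corresponding SAP tables plan subject-level n (%). It does not prescribe the overview, and protocol section 13.4 asks for a summary by intensity only where appropriate.

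**Conclusion.** The point holds as a weakness in a descriptive safety summary. In the overview, severity is expressed only against each treatment's own TEAE total, and no planned table gives the percentage of subjects with a severe TEAE across all terms, by treatment or overall. Under the assumed counts, a fourfold higher subject percentage (5.0% against 1.25%) prints as a lower event percentage (6.7% against 10.0%). That size depends on the counts, on about 80 subjects per treatment, and on one severe event per affected subject. What does not depend on them is that the planned percentage can order treatments either way relative to the risk per subject.

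The SDLP non-inferiority conclusion is not affected. A reader might also infer that relationship and withdrawal lack subject-level rows. They do not: the shell has both, and for withdrawal only the wording of the SAP section 10 bullet is out of step. The change is worth making because the better statistic needs no new data, not because the reported results would otherwise be unrecoverable.

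**What to change.** - Add to the SAP section 10 overview list and to Table 14.3.1.1: number and percentage of subjects by maximum TEAE severity. Use footnote [1], with the denominator being subjects dosed with that treatment, and count each subject once per treatment at the worst grade.
- Keep the counts of TEAEs by severity as a secondary description, preferably without percentages.
- Reword the withdrawal bullet in SAP section 10 to count subjects, as the shell already does.
- Leave relationship as it is: its subject-level row exists.

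The cost is a few lines of SAP text, one revised shell and a few reprogrammed rows, with no new data. If the event percentages are dropped, the event-level percentage distribution is no longer displayed, although it can still be worked out from the counts that remain.

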11. INTERIM ANALYSES AND DATA SAFETY MONITORING

There is no interim analysis or safety data monitoring planned for this study.

12. CHANGES TO PROTOCOL-SPECIFIED ANALYSES

There is no change from the planned analysis described in the protocol.

13. GENERAL INFORMATION RELATED TO DATA PRESENTATIONS

All programs used to generate statistical analyses will be validated according to Algorithme Pharma's standard operating procedures.

TFLs will be displayed on letter size paper, 8 ½ inches by 11 inches, using the Courier New font.

In general, summary statistics for raw variables (i.e., variables measured at the study site or central laboratory) will be displayed as follows: if required minima, maxima, means, quartiles, standard deviations and confidence limits will be displayed to the same number of decimal places as the raw data; if required medians will be displayed to one additional decimal place.

Percentages will be displayed to one decimal place. Percentages between 0 and 0.1 (exclusive) will be displayed as '<0.1'. P-values will be displayed to 3 decimal places. P-values that are less than 0.001 will be displayed as '<0.001'.

The numbers of decimal places for summary statistics of derived variables (i.e., variables that are not measured by the study site but are calculated for analysis based on other measured variables) will be determined on a case by case basis. In general, minima and maxima will be displayed to the commonly used unit of precision for the parameter. Means, medians, quartiles, and confidence limits will be displayed to one additional decimal place and standard deviations will be displayed to two additional decimal places.

The formats and layouts of TFLs are provided in subsequent sections. Actual formats and layouts may be altered slightly from those presented in the templates as necessary to accommodate actual data or statistics. Minor format changes will not require updates to the SAP.

The tables and listings listed below are common data displays. Their numbering and general content follow the ICH E3 guidelines. Some of the tables and listings may not be applicable/appropriate/necessary for a particular study. Additional tables and listings may be included, provided the numbering scheme remains consistent with ICH E3.

14. REFERENCE

PLANNED TABLES

Demographic Data

Table 14.1.1	Subject Disposition – All Subjects
Table 14.1.2.1	Summary of Demographic Characteristics (Safety Population)
Table 14.1.2.2	Summary of Demographic Characteristics (Intent-to-treat Population)
Table 14.1.2.3	Summary of Demographic Characteristics (Pharmacokinetic Population)

Efficacy Data

Tables in this section are based on the primary efficacy population unless otherwise stated.

Table 14.2.1.1	Standard Deviation of Lateral Position (SDLP)
Table 14.2.1.2.1	Standard Deviation of Lateral Position (SDLP) Analysis of Symmetry about Zero (ITT Population – Alprazolam versus Placebo)
Table 14.2.1.2.2	Standard Deviation of Lateral Position (SDLP) Analysis of Symmetry about Zero (ITT Population – Lasmiditan 50 mg versus Placebo)
Table 14.2.1.2.3	Standard Deviation of Lateral Position (SDLP) Analysis of Symmetry about Zero (ITT Population – Lasmiditan 50 mg versus Alprazolam)
Table 14.2.1.2.4	Standard Deviation of Lateral Position (SDLP) Analysis of Symmetry about Zero (ITT Population – Lasmiditan 100 mg versus Placebo)
Table 14.2.1.2.5	Standard Deviation of Lateral Position (SDLP) Analysis of Symmetry about Zero (ITT Population – Lasmiditan 100 mg versus Alprazolam)
Table 14.2.1.2.6	Standard Deviation of Lateral Position (SDLP) Analysis of Symmetry about Zero (ITT Population – Lasmiditan 200 mg versus Placebo)
Table 14.2.1.2.7	Standard Deviation of Lateral Position (SDLP) Analysis of Symmetry about Zero (ITT Population – Lasmiditan 200 mg versus Alprazolam)
Table 14.2.2.1	Visual Analog Scale (VAS) Motivation
Table 14.2.2.2	Visual Analog Scale (VAS) Self-appraisal
Table 14.2.3.1	Symbol Digit Coding (SDC) Number of Correct Responses
Table 14.2.3.2	Symbol Digit Coding (SDC) Accuracy
Table 14.2.3.3	Symbol Digit Coding (SDC) Standard Deviation of Reaction Time
Table 14.2.4.1	Driving Performance Lane Exceedance Number
Table 14.2.4.2	Driving Performance Lane Exceedance Maximum
Table 14.2.4.3	Driving Performance Lane Exceedance Duration
Table 14.2.4.4	Driving Performance Lane Exceedance Area of Exceedance
Table 14.2.4.5	Driving Performance Ratio Above Speed Limit
Table 14.2.4.6	Driving Performance Excessive Speed Count
Table 14.2.4.7	Driving Performance Excessive Speed Ratio
Table 14.2.4.8	Driving Performance Average Speed
Table 14.2.4.9	Driving Performance Speed Deviation
Table 14.2.4.10	Driving Performance Speed Count
Table 14.2.4.11	Driving Performance Speedings Ratio
Table 14.2.4.12	Driving Performance Excessive Ay (Cornering Speed Threshold Exceeded)
Table 14.2.4.13	Driving Performance Collision Count
Table 14.2.4.14	Driving Performance Off-road Crashes
Table 14.2.4.15	Driving Performance Total Collisions
Table 14.2.4.16	Driving Performance Divided Attention – Correct Responses
Table 14.2.4.17	Driving Performance Divided Attention – Omission Errors
Table 14.2.4.18	Driving Performance Divided Attention – Commission Errors

Table 14.2.4.19	Driving Performance Divided Attention – Reaction Time
Table 14.2.4.20	Driving Performance Divided Attention – Standard Deviation of Reaction Time
Table 14.2.5	Karolinska Sleepiness Scale (KSS)
Table 14.2.6	Self-Reported Readiness
Table 14.2.7.1	Plasma Concentration by Time Point (Safety Population)
Table 14.2.7.2	Correlation of In(Plasma Drug Levels) to SDLP
Table 14.2.7.3	Correlation of In(Plasma Drug Levels) to Visual Analog Scale (VAS) Motivation
Table 14.2.7.4	Correlation of In(Plasma Drug Levels) to Visual Analog Scale (VAS) Self-appraisal
Table 14.2.7.5	Correlation of In(Plasma Drug Levels) to Symbol Digit Coding (SDC) Number of Correct Responses
Table 14.2.7.6	Correlation of In(Plasma Drug Levels) to Symbol Digit Coding (SDC) Accuracy
Table 14.2.7.7	Correlation of In(Plasma Drug Levels) to Symbol Digit Coding (SDC) Standard Deviation of Reaction Time
Table 14.2.7.8	Correlation of In(Plasma Drug Levels) to Driving Performance Lane Exceedance Number
Table 14.2.7.9	Correlation of In(Plasma Drug Levels) to Driving Performance Lane Exceedance Maximum
Table 14.2.7.10	Correlation of In(Plasma Drug Levels) to Driving Performance Lane Exceedance Duration
Table 14.2.7.11	Correlation of In(Plasma Drug Levels) to Driving Performance Lane Exceedance Area of Exceedance
Table 14.2.7.12	Correlation of In(Plasma Drug Levels) to Driving Performance Ratio Above Speed Limit
Table 14.2.7.13	Correlation of In(Plasma Drug Levels) to Driving Performance Excessive Speed Count
Table 14.2.7.14	Correlation of In(Plasma Drug Levels) to Driving Performance Excessive Speed Ratio
Table 14.2.7.15	Correlation of In(Plasma Drug Levels) to Driving Performance Average Speed
Table 14.2.7.16	Correlation of In(Plasma Drug Levels) to Driving Performance Speed Deviation
Table 14.2.7.17	Correlation of In(Plasma Drug Levels) to Driving Performance Speed Count
Table 14.2.7.18	Correlation of In(Plasma Drug Levels) to Driving Performance Speeding Ratio
Table 14.2.7.19	Correlation of In(Plasma Drug Levels) to Driving Performance Excessive Ay (Cornering Speed Threshold Exceeded)
Table 14.2.7.20	Correlation of In(Plasma Drug Levels) to Driving Performance Collision Count
Table 14.2.7.21	Correlation of In(Plasma Drug Levels) to Driving Performance Off-road Crashes
Table 14.2.7.22	Correlation of In(Plasma Drug Levels) to Driving Performance Total Collisions
Table 14.2.7.23	Correlation of In(Plasma Drug Levels) to Driving Performance Divided Attention – Correct Responses
Table 14.2.7.24	Correlation of In(Plasma Drug Levels) to Driving Performance Divided Attention – Omission Errors
Table 14.2.7.25	Correlation of In(Plasma Drug Levels) to Driving Performance Divided Attention – Commission Errors

Table 14.2.7.26	Correlation of In(Plasma Drug Levels) to Driving Performance Divided Attention – Reaction Time
Table 14.2.7.27	Correlation of In(Plasma Drug Levels) to Driving Performance Divided Attention – Standard Deviation of Reaction Time
Table 14.2.7.28	Correlation of In(Plasma Drug Levels) to Karolinska Sleepiness Scale (KSS) Pre-Drive

Safety Data

Tables in this section are based on the safety population unless otherwise stated.

Table 14.3.1.1	Summary of Adverse Events
Table 14.3.1.2	Summary of Treatment Emergent Adverse Events by System Organ Class and MedDRA Preferred Term
Table 14.3.1.3	Summary of Serious Adverse Events by System Organ Class and MedDRA Preferred Term
Table 14.3.1.4	Summary of Treatment Emergent Adverse Events by System Organ Class and MedDRA Preferred Term and Maximum Severity
Table 14.3.1.5	Summary of Treatment Emergent Adverse Events by System Organ Class and MedDRA Preferred Term and Relationship To Study Drug
Table 14.3.2.1	Listing of Deaths, Other Serious and Significant Adverse Events
Table 14.3.2.2	Listing of Treatment Emergent Adverse Events Leading to Withdrawal
Table 14.3.4.1	Listing of Abnormal On-Study Laboratory Values
Table 14.3.4.2	Listing of Clinically Significant On-Study Laboratory Values
Table 14.3.4.3	Summary of Blood Chemistry
Table 14.3.4.4	Summary of Hematology
Table 14.3.4.5	Summary of Quantitative Urinalysis
Table 14.3.5.1	Listing of Abnormal On-Study Vital Signs Values
Table 14.3.5.2	Listing of Clinically Significant On-Study Vital Signs Values
Table 14.3.5.3	Summary of Vital Signs
Table 14.3.6.1	Listing of Abnormal On-Study ECG Assessments
Table 14.3.6.2	Listing of Clinically Significant On-Study ECG Assessments
Table 14.3.6.3	Summary of ECG Assessments
Table 14.3.7.1	Listing of Abnormal On-Study Physical Examination Findings
Table 14.3.7.2	Listing of Clinically Significant On-Study Physical Examination Findings

Planned Figures

Figure 14.2.1.1.1	Within Subject Difference Scores in SDLP by Treatment
Figure 14.2.1.2.1	Within Subject Difference Scores (Alprazolam - Placebo) (ITT Population - Alprazolam versus Placebo)
Figure 14.2.1.2.2	Within Subject Difference Scores (Lasmiditan 50 mg - Placebo) (ITT Population – Lasmiditan 50 mg versus Placebo)
Figure 14.2.1.2.3	Within Subject Difference Scores (Lasmiditan 100 mg - Placebo) (ITT Population – Lasmiditan 100 mg versus Placebo)
Figure 14.2.1.2.4	Within Subject Difference Scores (Lasmiditan 200 mg - Placebo) (ITT Population - Lasmiditan 200 mg versus Placebo)
Figure 14.2.7.2.1	Within Subject Difference Scores in SDLP by Plasma Concentration for Lasmiditan 50 mg
Figure 14.2.7.2.2	Within Subject Difference Scores in SDLP by Plasma Concentration for Lasmiditan 100 mg
Figure 14.2.7.2.3	Within Subject Difference Scores in SDLP by Plasma Concentration for Lasmiditan 200 mg
Figure 14.2.4.13	Collision Count
Figure 14.2.4.14	Off-road Crashes
Figure 14.2.4.15	Total Collisions

PLANNED LISTINGS

Listing 16.2.1	Listing of Study Disposition
Listing 16.2.3	Listing of Analysis Populations
Listing 16.2.4.1	Listing of Demographic Characteristics
Listing 16.2.4.2	Listing of Screen Failure Subjects
Listing 16.2.5.1	Listing of Investigational Product Administration
Listing 16.2.5.2	Listing of Lasmiditan Plasma Concentrations
Listing 16.2.6.1.1	Listing of Driving Simulator Part 1 of 5
Listing 16.2.6.1.2	Listing of Driving Simulator Part 2 of 5
Listing 16.2.6.1.3	Listing of Driving Simulator Part 3 of 5
Listing 16.2.6.1.4	Listing of Driving Simulator Part 4 of 5
Listing 16.2.6.1.5	Listing of Driving Simulator Part 5 of 5
Listing 16.2.6.2	Listing of Karolinska Sleepiness Scale (KSS)
Listing 16.2.6.3	Listing of CogScreen Symbol Digit Coding (SDC)
Listing 16.2.6.4	Listing of Visual Analog Scale (VAS)
Listing 16.2.7	Listing of Adverse Events
Listing 16.2.8.1	Listing of Blood Chemistry
Listing 16.2.8.2	Listing of Hematology
Listing 16.2.8.3	Listing of Urinalysis
Listing 16.2.8.4	Listing of Urine Drug Screen
Listing 16.2.8.5	Listing of Pregnancy Test
Listing 16.2.9.1	Listing of Alcohol Habits
Listing 16.2.9.2	Listing of Smoking Habits
Listing 16.2.9.3	Listing of Prior Medication
Listing 16.2.9.4	Listing of Concomitant Medication
Listing 16.2.9.5	Listing of Physical Examination
Listing 16.2.9.6	Listing of Vital Signs
Listing 16.2.9.7	Listing of ECG Assessments
Listing 16.2.9.8	Listing of Screening Summary
Listing 16.2.9.9	Listing of Medical History
Listing 16.2.9.10	Listing of Columbia-Suicide Severity Rating Scale (C-SSRS)
Listing 16.2.9.11	Listing of Epworth Sleepiness Scale
Listing 16.2.9.12	Listing of Simulator Sickness Questionnaire

